5.8. Analysis of Safety Data

The safety analysis will be performed on the SAF.

5.8.1. Analysis of Adverse Events

AE incidence tables will be presented for each treatment group, including the number (n) and percentage (%) of participants experiencing an AE, where multiple instances of the same event

occur in the same participant the event will be counted only once for that participant. The denominator for computation of percentages is the number of participants in each treatment group.

Treatment Emergent Adverse Events (TEAEs) are defined as AEs with either initial onset after the first dose of study treatment or that worsen after the first dose of study treatment. The number and proportion of participants reporting TEAEs will be summarized by SOC and PT.

Overall TEAE summary

The overall summary of TEAEs will be provided with number and proportions of participants with any:

- TEAEs
- Treatment-emergent serious adverse events (TE-SAEs)
- TEAEs of special interest (TE-AESI)
- Summary of deaths

TEAE incidence

Number and proportions of participants reporting TEAEs will be summarized for the following TEAEs:

- TEAEs
 - TEAEs by primary SOC and PT
 - TEAEs by primary SOC, PT and severity
 - TEAEs related to study drug by primary SOC and PT
 - Treatment-related TEAEs by primary SOC, PT and maximum severity
 - TE-AESI by primary SOC and PT
 - TEAEs leading to permanent treatment withdrawal by primary SOC and PT
- TE-SAEs
 - TE-SAEs by SOC and PT
 - Treatment-related TE-SAEs by primary SOC and PT
- TEAEs leading to death by primary SOC and PT

5.8.2. Assessment for Bleeding

Participants will be assessed for surgical site bleeding events at time points according to [Table 3](#). Description of surgical site bleeding events will include the following: onset and duration; associated clinical symptoms (if any) and sequelae, including prolonged hospitalization or deep wound infection; requirement for additional surgical or interventional procedure.

Participants will also be assessed for overall bleeding events at time points according to [Table 3](#). Description of bleeding events will include the following: location; onset and duration; associated symptoms (if any); precipitating factors (if any).

For all bleeding events (surgical and extra surgical), the following will be recorded: associated changes in hemoglobin, hematocrit; requirement for, timing of, and quantity of transfusion.

In addition, for all participants, peri- and post-operative blood loss will be recorded, as per local practice.

All bleeding events will need to be recorded as an AE with documentation sent to the central AC as instructed in the Study Manual for Venography and Event Reporting. Events will be classified by the AC using the ISTH criteria for both major ([Schulman, 2010](#)) and CRNM ([Kaatz, 2015](#)) bleeds as described in [Section 4.5.2](#).

5.8.3. Analysis of Clinical Laboratory Measurements

Laboratory measurements include clinical chemistry, hematology and urinalysis results, and will be converted to standard international units and US conventional units. Summaries of laboratory variables will include:

- Descriptive statistics of laboratory result and change from baseline by visit
- The number (n) and percentage (%) of participants with treatment-emergent PCSVs during study
- Shift tables based on baseline normal/abnormal may be used to present the results for parameters of interest

5.8.4. Analysis of Vital Signs

Summaries of vital sign variables will include:

- Descriptive statistics of vital sign variable and change from baseline by visit
- The number (n) and percentage (%) of participants with treatment-emergent PCSV, depending on data

5.8.5. Analysis of ECG

Summaries of 12-lead ECG parameters by treatment group will include:

- Each ECG parameter and change from baseline
- The number (n) and percentage (%) of participants with PCSV, depending on data
- ECG status (i.e. normal, abnormal) summarized by a shift table

5.8.6. Analysis of Pharmacokinetics Drug Concentration Data

The PK parameters may include, but are not limited to:

- C_{max} – peak concentration
- AUC_{last} -area under the curve computed from time zero to the time of the last positive concentration

The concentrations of total REGN9933 and total FXI over time will be summarized by descriptive statistics for each of the treatment groups for the purpose of estimating exposures in these groups. This descriptive statistical assessment will include the geometric means and ratios of the geometric means for selected PK parameters, as deemed appropriate.

5.8.7. Analysis of Immunogenicity Data

Immunogenicity variables described in Section 4.7 will be summarized by ADA status, ADA category and maximum titer observed in participants in the ADA analysis set. For samples confirmed as drug specific ADA positive, but found negative at the lowest titer dilution, the lowest dilution in the titer assay is imputed.

The ADA status of each participants may be classified as one of the following:

- Positive
- Pre-existing immunoreactivity: if the baseline sample is positive and all post baseline ADA titers are reported as less than 9-fold the baseline titer value.
- Negative: if all samples are found to be negative in the ADA assay.

The ADA category of each positive participants is classified as:

- Treatment-emergent ADA response: A negative results or missing result at baseline with at lease one positive post baseline result in the ADA assay.
- Treatment-boosted ADA response: A positive result at baseline in the ADA assay with at least one post baseline result ≥ 9 -fold the baseline titer value

Maximum ADA Titer category of each participants is classified as:

- Low (titer $< 1,000$)
- Moderate ($1,000 \leq \text{titer} \leq 10,000$)
- High (titer $> 10,000$)

The following will be summarized by treatment group and ADA titer level:

- Number (n) and percent (%) of ADA-negative participants
- Number (n) and percent (%) of pre-existing participants
- Number (n) and percent (%) of treatment-emergent ADA positive participants
- Number (n) and percent (%) of treatment-boosted ADA positive participants

5.8.8. Association of Immunogenicity with Exposure, Safety and Efficacy

Immunogenicity and Exposure

Potential association between immunogenicity and systemic exposure to REGN9933 will be explored by treatment groups. Plots of individual REGN9933 concentration time profiles may be provided to examine the potential impact of ADA category, maximum titer category.

Immunogenicity and Safety and Efficacy

Potential association between immunogenicity variables and safety may be explored with a primary focus on the following safety events during the TEAE period:

- Infusion reactions
- Hypersensitivity (SMQ: Hypersensitivity [Narrow])
- Anaphylaxis (SMQ: Anaphylactic Reaction [Narrow])

Potential association between immunogenicity variables and efficacy endpoints may be explored (e.g., scatter plot or spaghetti plot).

The safety and efficacy analyses mentioned above will be conducted using the following categories:

- ADA Positive
- Treatment-emergent
- Treatment-boosted
- Maximum post-baseline titer category in ADA positive participants

The association of immunogenicity with exposure, safety and efficacy analysis will be performed and reported separately.

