10.2.4. Infusion Reactions

Infusion reactions are defined as any relevant AE that occurs during the infusion or within 2 hours after the infusion is completed.

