11.2.1. Footnotes for the Schedule of Events

1. Assessments for this visit may be performed in the hospital if the participant has not yet been discharged.
2. If the participant is discharged prior to this visit, then information may be collected by telephone call, and assessments requiring blood draw may be omitted.
3. To be performed in women 55 years of age or younger.
4. Randomization will occur after completion of surgery on day 1.
5. Dosing will occur 12 to 24 hours after the end of surgery, and at least 12 hours after removal of the needle/catheter used for spinal/epidural anesthesia.
6. First dose will be given 12 to 24 hours after the end of surgery.
7. May include confirmatory studies for DVT of the leg or PE, as described in protocol Section 9.2.2.2. Confirmatory studies for suspected DVT of the leg or PE may be required more than once, per the discretion of the investigator.
8. Refer to Table 4 for detailed information on Visit 2 samples.

9. Samples for ADA must be collected prior to dose administration on the same day that study drug is administrated. Refer to Table 4.
10. The genomics sub-study informed consent form (ICF; for RNA and DNA analysis) must be signed prior to performing this sample collection.
11. Samples for DNA extraction should be collected at the baseline visit (predose) but may also be collected at any later study visit.

Table 4: Schedule of Events: Visit 2 Blood Collection

Baseline Visit 2 (Day 1)			
Study Procedure	Pre-operatively	Post-operatively	
		Pre-dosing Up to 1 hour prior to dosing	Post-dosing REGN9933 only: as close as possible to 1- hour post-dose
Laboratory Testing			
Hematology	X ¹		
Blood chemistry	X ¹		
Coagulation panel	X ¹		
Urinalysis			
Pharmacokinetics and Immunogenicity Sampling			
Drug concentration sample (REGN9933)		X ²	X ²
ADA (REGN9933)		X ²	
Plasma for total FXI concentration	X ¹	X ³	X ²
Biomarkers			
Plasma for aPTT, PT (central lab)	X ¹	X ³	X ²
Plasma for FXI activity (FXI:C) and TGA	X ¹	X ³	X ²
Serum for exploratory research	X ¹	X ³	
Plasma for exploratory research	X ¹	X ³	

ADA: anti-drug antibody; aPTT: activated partial thrombin time; FXI: Factor XI; FXI:C: Factor XI functional activity; PT: prothrombin time; TGA: thrombin generation assay

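### The ADA-safety and ADA-efficacy groupings in SAP 5.8.8 all need a post-dose ADA result, scheduled only at day 75, so they cannot address infusion reactions or show that ADA preceded VTE through day 12; the pre-dose result should be added as a grouping.

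*SAP*

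**What the plan says.** SAP 5.8.8 allows exploration of ADA against safety, with infusion reactions, hypersensitivity and anaphylaxis as the main events, and against the efficacy endpoints. The exploration is optional, but the grouping is fixed: "The safety and efficacy analyses mentioned above will be conducted using the following categories". Four groupings follow: ADA positive, treatment-emergent, treatment-boosted, and "Maximum post-baseline titer category in ADA positive participants".

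SAP 5.8.7 supplies the definitions.

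- Positive, pre-existing immunoreactivity and negative are alternative statuses. Positive participants are divided into treatment-emergent and treatment-boosted.
- Treatment-emergent: "A negative results or missing result at baseline with at lease one positive post baseline result in the ADA assay".
- Treatment-boosted: "A positive result at baseline in the ADA assay with at least one post baseline result" at least 9 times the baseline titer.
- Pre-existing: "if the baseline sample is positive and all post baseline ADA titers are reported as less than 9-fold the baseline titer value".

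The schedule (SAP 11.2, Tables 3 and 4) has two ADA samples, one pre-dose at Visit 2 and one at Visit 6. On the first, SAP 11.2.1 states: "Samples for ADA must be collected prior to dose administration on the same day that study drug is administrated". Visit 6 is day 75, with a window of day 70 to 80 (SAP 6.4). Withdrawn participants have the end-of-study assessments at an early termination visit instead (Protocol 9.1.2).

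REGN9933 is given once. Protocol 10.2.4 fixes the timing of the first named safety event: "Infusion reactions are defined as any relevant AE that occurs during the infusion or within 2 hours after the infusion is completed". The primary VTE endpoint closes at day 12 (SAP 4.4.1).

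**The concern.** A table of infusion reactions by ADA group is useful only if the group reflects antibody that was present at the infusion. There is one infusion, so a response that develops afterwards never meets a second dose at which it could provoke a reaction. Yet every listed group is set by a sample taken after the only infusion, normally about ten weeks after it.

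For VTE through day 12 the problem is milder but similar. The grouping is read two months after the outcome has closed, so an association, or its absence, says nothing about which came first.

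Meanwhile the one ADA measurement known to precede both outcomes, the pre-dose sample, is not a grouping in its own right. At stake is whether an exploratory analysis can answer the question it sets itself.

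**Working it through.** The documents give no figure on this point to reproduce. The check has three parts.

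**1. Timing.** Inputs: end-of-study window, day 70 to 80 (SAP 6.4); VTE cut-off, day 12 (SAP 4.4.1); infusion-reaction window, up to 2 hours after the infusion (Protocol 10.2.4); first dose 12 to 24 hours after surgery on day 1 (SAP 2.1), hence day 1 or 2.

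- End of study minus day 12: 75 − 12 = 63 days nominal; 70 − 12 = 58 to 80 − 12 = 68 days across the window.
- End of study minus infusion day: 70 − 2 = 68 to 80 − 1 = 79 days, about 10 to 11 weeks.
- An early termination sample can shorten these gaps, but it still comes after the infusion.

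**2. Classification.** The SAP 5.8.7 rules were applied to each combination of baseline and post-baseline result, using an illustrative baseline titer of 30, so that 240 is 8-fold and 270 is 9-fold.

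| Pre-dose | Post-dose | Class under 5.8.7 | In a 5.8.8 group? |
|---|---|---|---|
| Negative or missing | Negative | Negative | No |
| Negative or missing | 30, 240 or 270 | Treatment-emergent | Yes |
| 30 | Negative, 30 or 240 | Pre-existing | No |
| 30 | 270 | Treatment-boosted | Yes |
| Any | None | Outside the ADA analysis set (SAP 3.4) | No |

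Entry to any listed group always turns on the post-dose result. A participant who is positive before dosing enters only if the later titer is at least 9-fold. ADA-negative participants, the natural comparator, are not on the list either. The last row matters as well: someone who reacts to the infusion and leaves without another ADA sample is dropped from the ADA analysis set, even with a valid pre-dose result.

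**3. Likely numbers.** Neither document gives a rate of pre-dose positivity, so a range is assumed. Expected count = 120 × rate. The chance of at least 5 is the upper tail of a binomial with n = 120.

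| Assumed rate | Expected baseline-positive | Chance of at least 5 |
|---|---|---|
| 1% | 1.2 | 0.7% |
| 3% | 3.6 | 29% |
| 5% | 6 | 72% |
| 10% | 12 | 99% |

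These counts cover all baseline-positive participants. Those later boosted would already be in a listed group, so the number in no group is at most this.

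**The case against.** Several points on the other side are right and limit the claim.

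- A reader might infer that pre-existing immunoreactivity is the one status that precedes the infusion and is all that needs adding. The SAP does not support that: the status also requires every later titer to be below 9-fold, so it too is settled by the post-dose sample. What precedes dosing is the pre-dose result itself.
- A reader might infer that the baseline result is ignored altogether. It is not. It separates treatment-emergent from treatment-boosted, and boosted participants were positive before dosing. The omission is confined to baseline-positive participants who are not boosted.
- It is tempting to say that ADA found at day 75 cannot explain a VTE by day 12. That confuses detection with onset. With no sample at day 5, 10 or 30, the antibody could have appeared before day 12. The supportable statement is only that the day-75 result cannot show the order.
- The listed categories suit other outcomes in scope. Treatment-emergent events are counted through end of study (Protocol 4.1.2), as are several exploratory efficacy endpoints (SAP 4.4.3).
- Pre-existing status is not lost: SAP 5.8.7 counts it and Protocol 11.4.7 promises participant listings. Neither, however, links it to events.
- The work is optional and reported separately, and with few baseline-positive participants a listing may be all the data allow.

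SAP 5.8.7 also never defines positive. That it excludes pre-existing is inferred from the either-or list of statuses and from the two categories given for positive participants. If the sponsor meant otherwise, that needs saying.

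None of this answers the objection on infusion reactions, where the timing rules out a causal reading of a later response.

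**Conclusion.** The point holds, at low severity. All four listed groupings require a post-dose ADA result. For infusion reactions they cannot inform the question; for VTE through day 12 they cannot establish which came first. For later adverse events, end-of-study efficacy and late drug concentrations they are appropriate.

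The time-order defect does not depend on prevalence. The number of people affected does: about 1 to 12 baseline-positive participants if 1% to 10% of 120 are positive before dosing, which is an assumption. No primary or secondary efficacy result changes. Nor does this amount to a fault in the sampling schedule, since the sample that the better grouping needs is already planned.

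**What to change.** In SAP 5.8.8:

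- Add the pre-dose ADA result, positive versus negative whatever the later titer, as a grouping for infusion reactions, for hypersensitivity and anaphylaxis around the infusion, and for VTE through day 12. The pre-dose-negative group also supplies the missing comparator.
- For this grouping, use all dosed REGN9933 participants with a pre-dose result. State that this departs from the ADA analysis set in SAP 3.4, which requires a post-dose result.
- Keep the four existing categories for later events, end-of-study efficacy and late concentrations.

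The cost is a few lines of SAP text and one small table or listing. No visit, sample or primary analysis changes. The drawback is small groups, so the output should be labelled descriptive and given as a listing if only a handful of participants are baseline-positive.

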5.8.9. Analysis of Pharmacodynamic and Exploratory Biomarker Data

The analysis of Pharmacodynamic and Biomarker will be performed in the PD analysis set using all observed data.

For biomarkers including aPTT, PT, FXI:C and thrombin generation (following intrinsic and extrinsic pathway activation), the following descriptive data will be generated: raw data at baseline, by treatment group, and overall. Biomarkers measured post-treatment will be summarized over time. Change, percent change, and/or fold change from baseline to each scheduled assessment time will be summarized by treatment with descriptive statistics if deemed appropriate.

TGA for extrinsic and intrinsic pathways will be analyzed separately.

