4.1.2. Secondary Endpoints

The secondary endpoints are:

- Incidence of major bleeding and CRNM bleeding (defined in Section 5.3.1) through time of venography (or day 12, whichever is earlier)
- Incidence of treatment-emergent adverse events (TEAEs) through the end of study
- Incidence of major VTE (defined in Section 5.2.2) through day 12 (REGN9933 versus enoxaparin)
- Incidence of DVT as measured by venography of the operated leg on day 10 ± 2 days (REGN9933 vs enoxaparin)
- Concentrations of REGN9933 in serum through end of study
- Change in aPTT from baseline through end of study
- Change in PT from baseline through end of study
- Incidence and titer of anti-drug antibodies (ADA) to REGN9933 through end of study
- Incidence of confirmed, adjudicated VTE through day 12 (enoxaparin vs apixaban)

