8.2. Rescue Treatments

8.2.1. Treatment of VTE

Treatment of symptomatic VTE events that occur during the trial will be managed by the investigator per local practice.

For participants receiving either enoxaparin or apixaban, increasing the dose of either agent to therapeutic levels (according to local standards) may be considered. For participants who develop a symptomatic VTE after receiving REGN9933, consideration may be given to DOACs, which have more predictable anticoagulant activity and lower bleeding liability than other anticoagulants. Therapeutic doses of LMWH may also be considered.

Asymptomatic VTE may be monitored with additional imaging assessments at the discretion of the site investigator. In addition, treatment with therapeutic anticoagulation may be considered, depending on the clinical situation, and at the discretion of the site investigator.

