8.2.2. Treatment of Bleeding Events

Participants requiring emergent evaluation for bleeding should be first treated with conventional bleeding management per standard protocols, including local compression by either manual compression or pressure bandages applied to the wounds. If bleeding persists, treatment should be provided at the discretion of the treating physician and aligned with local practice and bleeding management guidelines. Participants should be treated with respect to their clinical signs and symptoms of bleeding and not treated per a normalized aPTT/PT laboratory value nor per a specific FXI activity level.

Of note, activated Factor VII (Factor VIIa) products have been reported as successful bypass agents to control bleeding in FXI-deficient patients. Factor VIIa, through multiple portions of the coagulation cascade, contributes to activation of thrombin (Factor IIa) without need for FXI. Factor VIIa is clinically available as recombinant Factor VIIa (rFVIIa) under the brand name NovoSeven ([NovoSeven \(Summary of Product Characteristics\), 2021](#)).

If NovoSeven or another Factor VIIa formulation is available and selected for use at the discretion of the treating physician, the literature has commonly reported NovoSeven doses of 15 µg/kg to 30 µg/kg administered as an IV bolus in FXI-deficient patients. NovoSeven has a half-life of approximately 3 hours and repeat doses of NovoSeven have been reported as administered 2 hours to 6 hours following the first dose depending on surgical and bleeding circumstances. Continuous infusions of rFVIIa at 1.8 µg/kg to 3.6 µg/kg have also been utilized in clinical practice. These lower doses of NovoSeven have been administered with or without anti-fibrinolytics such as tranexamic acid.

Treatment with rescue medications in these events may impact the aPTT and other PD-related endpoints.

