8.8.2. Permitted Medications

Use of standard-of-care medications not listed as prohibited will be allowed.

For subjects assigned to either the enoxaparin or apixaban treatment arm, continued VTE prophylaxis (after completion of protocol-defined treatment, ie through the day of venography [or day 12, whichever is earlier]) is permitted, if deemed necessary by the site investigator based on local guidelines and/or clinical judgment. For the choice of agent to be used for subsequent VTE prophylaxis, it is preferred that the originally assigned treatment (ie enoxaparin or apixaban) is used. However, it is permissible to use other agents, as long as they are consistent with local regulations and standard of care for VTE prophylaxis after TKA surgery.

COVID-19 vaccination and any other vaccination can be administered as deemed necessary per the investigator based on his/her practice, standard of care, or as required based on mandatory vaccination programs. Vaccination is suggested to be administered preferably at least 1 week before the first dose of study drug (Section 7.2.2 Exclusion criterion 22), or at the earliest, 21 days following the last dose of study drug. Live-attenuated vaccines are generally not recommended during the study; however, use is allowed per the investigator's discretion.

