3.5. Pharmacodynamic Analysis Sets

The pharmacodynamic analysis set (PDAS) includes all randomized participants who received any study drug and who had at least 1 non-missing PD result following the first dose of study drug; it is based on the treatment received (as treated).

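### The aPTT, PT, FXI:C and TGA summaries to day 75 pool values taken on rescue, therapeutic or extended anticoagulants, and the SAP has no flag or companion summary to separate them

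*SAP*

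**What the plan says.** The secondary endpoints in Protocol 4.1.2 include "Change in aPTT from baseline through end of study" and "Change in PT from baseline through end of study". Protocol Table 2 schedules central-laboratory aPTT, PT, FXI:C and TGA samples at Visit 2 and at days 5, 10, 30 and 75. Protocol 11.4.8 leaves further biomarker detail to the SAP.

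The data rule in SAP 5.8.9 is: "The analysis of Pharmacodynamic and Biomarker will be performed in the PD analysis set using all observed data". Changes from baseline "will be summarized by treatment with descriptive statistics if deemed appropriate". The PD set in SAP 3.5 takes treated participants "who had at least 1 non-missing PD result following the first dose of study drug", with no on-treatment restriction.

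The protocol allows other clotting-active drugs during this period:

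- **VTE treatment, any arm (8.2.1).** For asymptomatic VTE, "treatment with therapeutic anticoagulation may be considered, depending on the clinical situation". For symptomatic VTE after REGN9933, DOACs or therapeutic LMWH may be considered. Section 8.8.1 allows anticoagulants in that arm only to treat an AE.
- **Extended prophylaxis, comparator arms only (8.8.2).** The assigned drug is preferred, but "it is permissible to use other agents, as long as they are consistent with local regulations and standard of care". Section 3.2.1 prohibits prophylactic anticoagulants in the REGN9933 arm.
- **Bleeding rescue (8.2.2).** Factor VIIa is the agent discussed, followed by the warning: "Treatment with rescue medications in these events may impact the aPTT and other PD-related endpoints".

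**The concern.** The secondary PD objective is the effect of REGN9933 on the intrinsic pathway (aPTT) and the extrinsic pathway (PT). Protocol 9.2.6.1 expects PT to be unaffected. Protocol 3.2.2 reports aPTT back within 10% of normal 64 days after a 300 mg dose. Both readings concern small or absent changes, so a minority of values taken on another anticoagulant can blur them.

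The comparator arms have a separate problem. Protocol 3.2.1 reasons that enoxaparin and apixaban are not at relevant levels a few days after the last dose. Continued prophylaxis under 8.8.2 removes that assurance for the day-30 sample.

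Treatment for VTE also follows the efficacy outcome. Affected values therefore cluster among participants with events, which matters for the exploratory look at PK, biomarkers and efficacy.

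**Working it through.** The plan states no figure for the PD endpoints, so there is none to reproduce. The check is whether any rule separates these values, and then how many participants could be affected.

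**1. Is there a rule?** SAP 3.5 and 5.8.9 contain none. SAP 6.2 to 6.4 deal with quantification limits, missing data and visit windows. SAP 5.3 allows an optional tabulation of anticoagulants outside assigned treatment, but does not link it to PD values. SAP 4.3 repeats the prohibitions and does not carry over the permission for extended prophylaxis.

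**2. Which samples can be affected?** Venography is at day 10 ± 2, so treatment prompted by it mainly precedes the day-30 and day-75 samples. The day-30 window is 27 to 33. Protocol 3.2.1 cites labelled enoxaparin use up to 35 days, which covers that window.

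**3. How many in the REGN9933 arm?** Inputs: about 120 per arm and a 13% VTE rate (Protocol 11.2); fewer than 2% with symptomatic VTE in comparable FXI trials (Protocol 3.3.1).

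- All VTE treated: 120 × 0.13 = 15.6 participants (13%).
- Only symptomatic VTE treated: at most 120 × 0.02 = 2.4 participants (2%).

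The share exposed through VTE treatment is therefore roughly 2% to 13%, because treating asymptomatic VTE is optional.

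**4. How many in the comparator arms?** Enoxaparin: 120 × 0.224 = 26.9 expected VTEs. Extended prophylaxis is at the site's discretion and could reach any share up to 100%.

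**5. Scale of an aPTT shift.** For samples where the underlying fold change is near 1, shift in arm mean = share exposed × (f − 1). Here f is the fold change produced by the other drug. The documents do not give f; 1.1 to 1.5 is an assumption.

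| Arm | Share exposed | f = 1.1 | f = 1.5 |
|---|---|---|---|
| REGN9933 | 2% | 0.002 | 0.010 |
| REGN9933 | 13% | 0.013 | 0.065 |
| Comparator | 50% | 0.05 | 0.25 |
| Comparator | 100% | 0.10 | 0.50 |

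Against the early REGN9933 effect of about 2.8-fold (Protocol 3.2.2), 0.065 is negligible. Against a late residual of about 0.10, it is not: 0.065 / 0.10 = 65% at the top of the range and 0.002 / 0.10 = 2% at the bottom.

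**6. Scale of a PT shift.** With an assumed lengthening of 3 to 12 s in exposed participants, also not in the documents, the REGN9933 mean moves by 0.02 × 3 = 0.06 s to 0.13 × 12 = 1.56 s. The width of that range shows how far the answer depends on the assumption.

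**The case against.** The strongest reply is that little inference is at risk. The aPTT and PT analyses are descriptive, with no test or decision threshold. SAP section 5 requires medians, quartiles and extremes beside the mean. With at most about 13% exposed, the median moves little and an affected tail would show in the maximum. Days 5 and 10 largely precede treatment prompted by the venogram and fall within the expected period of maximal effect, so the main PD reading is mostly protected. An all-observed summary is also a legitimate choice for an endpoint defined to end of study, and excluding values selects on VTE or bleeding. All of this stands. It limits the importance of the point and argues against replacing the all-observed summary. It does not supply a way to separate the late values.

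Three stronger readings are tempting, and the documents do not support them:

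- **That the protocol says rescue and extended anticoagulants alter these assays.** Its warning is that rescue may do so, and it concerns bleeding events. Factor VIIa, discussed there, is procoagulant. Nothing similar is said about VTE treatment or extended prophylaxis.
- **That extended prophylaxis could create a false REGN9933 effect within its arm.** It is prohibited there. Only treatment of an AE could have that result, in a minority. At day 30 the drug's own aPTT effect is still expected, since Protocol 3.2.1 puts it through at least day 35.
- **That the PT shift amounts to many standard errors.** The documents give neither an SD nor a PT effect. A mixture of exposed and unexposed values would also inflate the SD, so an error computed from unaffected values would overstate the ratio.

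**Conclusion.** The gap is real and modest. Followed as written, SAP 5.8.9 mixes other drugs' effects into the day-30 and day-75 summaries and gives the reader no means of seeing how much. In the REGN9933 arm roughly 2% to 13% of participants could be affected, mainly in PT at both late visits and in residual aPTT at day 75. In the comparator arms, day-30 values could largely describe the extended agent used.

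The participant counts rest on the plan's assumed VTE rates and on the symptomatic share it cites from comparable trials. They do not count bleeding rescue or anticoagulation for other AEs. The sizes of the shifts rest on assumed assay effects and serve only as scale. The primary endpoint is not touched.

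**What to change.** In SAP 5.8.9:

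1. Derive a flag from concomitant-medication dates for each PD value taken after the start of any therapeutic-dose, non-assigned or extended anticoagulant, or of Factor VIIa.
2. Present a summary of aPTT, PT, FXI:C and TGA excluding flagged values beside the all-observed summary.
3. Report the number flagged by arm and visit.
4. Mark flagged values in PK-PD plots.

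The cost is SAP wording, one derived variable and a second set of descriptive tables. SAP 4.3 already has medications recorded to the end-of-study visit, so no new collection is needed and no clinical rule changes. The exclusion summary will have fewer values at days 30 and 75, possibly many fewer in the comparator arms at day 30, and some selection by VTE or bleeding status. Keeping the all-observed summary beside it makes both visible.
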